2.0 Objectives

Aim 1 (Phase 1). Refine a treatment protocol for preoperative education and training and postoperative application of VR-BF in children and adolescents undergoing surgery. We will collect qualitative feedback (regarding content, usability, perceived benefits) via questionnaires and a semi-structured interview and sensitivity to change of key physiological parameters (heartrate variability, respiratory rate) from 12-32 patients (12-18 years) undergoing surgery anticipated to cause moderate to severe pain. Purposive sampling will be used to obtain a representative sample of a broad patient population. Treatment protocol refinement using iterative methodology will allow us to define the trial protocol, including frequency and duration of **(1a)** preoperative education and training and **(1b)** postoperative administration of VR-BF.

Feasibility and Acceptability of Technology-Based Interventions in the Perioperative Setting

Aim 2 (Phase 2). Conduct a pilot randomized controlled trial to assess the feasibility and acceptability of perioperative use of VR-BF in children and adolescents undergoing surgery. Seventy children and adolescents (12-18 years) scheduled for surgeries anticipated to cause moderate to severe pain will be randomized to receive VR-BF or active control (commercially available *Manage My Pain* application). *Manage My Pain* is engaging but lacks specific instruction in behavior change techniques, a key feature of VR-BF. It is included as the control arm to confirm appropriateness for use in the future efficacy trial. Specifically, (2a) Feasibility will be assessed by rates of study recruitment, enrollment and randomization, retention, and adherence. Target goals will be set at 80% for each assessment. (2b) Acceptability will be assessed by treatment/study burden, satisfaction, treatment credibility, and tolerability. It is essential that both treatment arms are feasible and acceptable for use in an efficacy trial.

Our central hypothesis is that preoperative education and training combined with independent, self-directed, repeated postoperative use of VR-BF will be feasible and acceptable in this population. This proposal addresses key components necessary for the design of a large-scale, clinical efficacy trial.

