Study population. Subjects will be recruited when scheduled for surgery at Nationwide Children's Hospital. We will coordinate recruitment efforts with surgeons who perform surgeries that require pain management by the Acute Pain Service. We will screen patient lists provided by the surgical schedulers as well as operating room schedules to identify potentially eligible patients prior to their scheduled surgery. Messages assessing interest in the study will be sent through MyChart. We anticipate recruiting 1 patient per week. We are confident that we can successfully recruit and enroll our full cohort of up to 102 patients: up to 32 for Aim 1 (minimum 12 patients) and 70 for Aim 2.

Blinding. Although patients will not be blinded to the intervention they receive, patients and families will be blinded with respect to the study arms. Therefore, the consent will describe the study as assessing technology-based interventions for the management of pain without specific detail about VR-BF (FOREVR VR) or *Manage My Pain* or indicate the use of any device, such as a headset. Once assigned to a group, patients will receive a handout describing the intervention with instructions and information about what participation entails. We will also blind data collection by using a study number for each patient and will not indicate in which arm the patient is enrolled in data collection forms. The biostatistician will be blinded to the patient groups during analysis.

Study Materials

Self-reported measures. Patients will be asked to complete a survey at the end of study participation as well as participate in a semi-structured interview. Parents will also be asked to complete a survey. The questionnaires will be completed through the Research Electronic Data Capture (REDCap) database.

Feasibility and Acceptability of Technology-Based Interventions in the Perioperative Setting

VR headset. Participants will use the Oculus/Meta Quest VR headset with the FOREVR VR device. When necessary, we will use the software supplied by Invincikids (*Mindful Aurora* application) with the Oculus/Meta Quest.

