The Oculus/Meta Quest VR devices are non-invasive, relaxation devices that are commercially and widely available to deliver mobile (untethered) VR content to the patient; they are not FDA regulated. Both devices are all-in-one headsets, so no additional hardware is required to deliver the VR experience. These devices have audio capabilities built into the headset to deliver instructions and application sounds, creating an immersive experience. We have used these devices in multiple IRBs since 2018 without any adverse events. Each VR headset will be cleaned with an alcohol or peroxide wipe according to infection control standards following use of the device by the patient as well as prior to use for each patient and may undergo further cleaning with UV light using the Cleanbox (<https://cleanboxtech.com/>).

VR session. All participants will receive a device tutorial at the start of the study which will entail teaching them how to use the device and introducing them to the VR-BF software. They will be taught how to sync their breathing with the application. Patients will be instructed to remove the device should any discomfort or side effects occur, such as motion sickness, dizziness, or nausea.

FOREVR VR. FOREVR VR is the result of the collaboration between our research team, engineers at the Digital Experience (DX) Center at Cincinnati Children's Hospital, and programmers at House of Moves, an animation and motion capture studio in Los Angeles, California. FOREVR VR integrates real-time patient physiological data into a gamified environment using a chest strap (to monitor respiration) and an ear clip (adapted from HeartMath, see below) to measure heart rate. This technique is effective in reducing respiratory rate, and consequently, increasing heartrate variability.^{20,97} This increased heartrate variability increases vagal tone, resulting in activation of the parasympathetic response and decreased pain.⁹⁷

VR-BF content. We currently have two game options for use with the FOREVR VR device. The first is a 360-video shot in Eden Park (a public park in Cincinnati, OH) that starts out as a stand-still, black and white image that adds color and eventually motion as the participant achieves target heart rate and respiratory rate targets. The second is a blooming flower scene that starts with a clean, blank scene that allows the participant to have a flower appear and fully bloom as he/she achieves target physiological parameters.

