In this scenario, the *Mindful Aurora* application would be used to deliver the VR content. This application acts as an escape for patients as well as a tool to help them learn slow breathing and relaxation techniques. It transports patients to an alpine meadow. With the help of a 10-minute relaxation narrative, study participants will observe the world transition from day to night while focusing on paced breathing. The goal of the application is to have participants mirror the rate of their breathing with the virtual world around them, which includes changes in floating butterflies and swaying trees to assist in the pacing of their breathing. This technique is effective in reducing respiratory rate, and consequently, increasing heartrate variability.^{20,97} This increased heartrate variability increases vagal tone, resulting in activation of the parasympathetic response and decreased pain.⁹⁷ This is the same application that has been used to deliver VR-BF content in **CCHMC IRB #2018-2892, 2019-1090, and 2020-0258.**

Manage My Pain. Control patients in Aim 2 will use the *Manage My Pain* application analogously to VR-BF per the protocol developed in Phase 1. This commercially available application is designed to assist patients with recognizing and reflecting on their pain and is highly engaging. It is available for iPhone, Android, and laptop download and is approved for children 12 years of age and older. In an assessment of commercially available pain applications, *Manage My Pain* was found to be appropriate for adolescents and had a high engagement score (4.2/5) as well as an excellent functionality rating (4.5/5).¹¹⁴ While it scored high overall (application quality score 4.06/5), it lacks the immersion and specific instruction in behavior change techniques,¹¹⁴ which are key features of VR-BF.

Device Tracking. Participants in Phase 1 as well as those randomized to the VR group in Aim 2 will receive a VR headset and FOREVR VR device to take home. During the first visit, these patients and families will be told that they will be given temporary possession of this equipment. To help increase our ability to retrieve these devices, they will be asked to sign a Device Agreement form. We will plan to collect the devices in the first postoperative clinic visit. If this is not possible, we will provide patients with a prepaid label and box to mail the device back to us. Other arrangements may be made with families for device retrieval as necessary.

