sampling will be used to select a representative patient group according to age, sex, and race. We anticipate recruiting about 1 patient per week. Patients will be identified when scheduled for surgery. They will receive scripted instruction on the Oculus/Meta Quest and a tutorial on the biofeedback application. Once device and content education are complete, patients will receive manual-based training on the benefits of HRV BF.⁵⁶ They will be given the appropriate equipment and instructed to complete an independent daily, 10-minute session (based on the standard duration of a BF session) and record each session in a log. Patients will bring the equipment to the hospital on the day of surgery for continuation into Aim 1b. After surgery, patients will have free use of VR-BF. They will be instructed to undergo, at minimum, one daily, 10-minute session. They will also be instructed to freely use VR-BF, particularly when in pain. They will use a log to record their VR-BF usage (date, time, and duration). Patients will be visited daily, or more or less frequently as applicable/needed, to assist with log completion and any issues. On the day of discharge, a study team member will conduct a detailed, semi-structured interview. Patients may take the VR-BF device home for up to two weeks for home pain management; a similar log will be used to document home use. We will enroll 4 patients at a time and analyze data to refine the protocol in an iterative fashion; this process will be repeated until 12 patients are enrolled. If further data is required for protocol refinement, we will continue recruiting patients in groups of 4 as necessary until a maximum number of 32 patients is reached.

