15.0 Risks to Subjects*

There are minimal physical risks to participants and enrollment in this study will not alter their management. All patients will receive pain management per the Acute Pain Service during the duration of the study.

Clinical Care. Enrolled patients will receive the same care and attention in the postoperative period or during their hospital stay as those non-enrolled patients. Patients will be given the opportunity to end participation in the study at any time.

VR Headset. VR headsets used in this study are minimal risk devices, and because they are considered a relaxation device by the FDA, they are not regulated. Risks specific to this research study are minimal or absent with the greatest risk being motion sickness while the headset is in place¹¹³ and a theoretical risk of inducing seizures (0.025% in pediatric data supplied by a similar Samsung device). Should motion sickness occur, the participant will be instructed to remove the device to ensure resolution of symptoms; we will exclude patients with a history of seizure disorder or other relevant neurological conditions. Other adverse events will be defined using standard criteria. The researchers shall monitor the patient while the device is applied. Serious adverse events, although unanticipated, will be reported using routine avenues. The Starlight Xperience device was used in our pilot study (**CCHMC IRB #2018-2892**) without any documentation of adverse effects. We have since purchased new headsets, the Oculus Quest and Oculus Quest 2, which have been used in prior studies without any reported adverse events (**CCHMC IRBs #2019-1090, 2020-0258, 2020-0612**). We will continue updating to newer versions of the Oculus/Meta Quest as they become available when new equipment is required.

FOREVR VR. This device has been approved for both research and clinical use by the Equipment and Standards Committee at Cincinnati Children's Hospital. It is a noninvasive device to measure respiratory rate (via chest movement) and heart rate using an ear clip. This device is also considered a minimal risk device. This is the first study to use FOREVR VR.

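### The Risks section promises researcher monitoring whenever the headset is worn, but most VR-BF sessions are unattended, and no described log has a place for symptoms

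*Combined protocol and SAP*

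**What the plan says.** Section 15.0 (VR Headset) names motion sickness as the greatest risk and mentions a theoretical seizure risk. It then gives two safeguards: "Should motion sickness occur, the participant will be instructed to remove the device to ensure resolution of symptoms", and "The researchers shall monitor the patient while the device is applied". The second has no limit by place or phase.

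The rest of the protocol describes use without staff:

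- Section 2.0 frames the central hypothesis around "independent, self-directed, repeated postoperative use of VR-BF".
- Section 6.0 (Device Tracking) says that VR patients "will receive a VR headset and FOREVR VR device to take home".
- Section 6.0 (Aim 1 Research Design) has them "instructed to complete an independent daily, 10-minute session" before surgery. Section 9.0 sets this period at one week.
- In hospital, staff visit daily or as needed to help with logs and problems. Home use after discharge is optional, for up to two weeks.

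On recording, the Tolerability text in section 6.0 undertakes to count minor and moderate/severe adverse effects, and Table 3 lists adverse events as additional tolerability data. The Additional Data Collection text names adverse events among items that may go in the case report form (CRF). Section 17.0 reports the number and percentage of patients with adverse events, with a 95% CI, and compiles tolerability from questionnaires and interviews.

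**The concern.** A safeguard for patients aged 12 to 18 is stated in the Risks section beside the two named headset hazards, and the trial cannot deliver it for home or self-directed sessions. Anyone judging the risk from that section would believe that a researcher is present whenever the headset is on.

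The second consequence is smaller. If nobody is watching, a mild symptom becomes data only if the patient writes it down, reports it, or recalls it when asked. The plan describes only part of that chain. What is exposed is the descriptive adverse-event rate for repeated, unattended use. That rate is new information: the pilots in section 3.0 saw no adverse effects, but each gave a single 10-minute session, and this is the first study to use FOREVR VR.

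**Working it through.** The plan gives no figure on this point to reproduce. The sample-size calculation in section 17.0 concerns an 80% proportion and is not involved.

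**Step 1. The monitoring sentence against each period of use.**

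| Period | Researcher present? | Source |
|---|---|---|
| Tutorial and training | Yes, though the visit may be virtual | 6.0, 9.0 |
| Home practice, one week before surgery | No | 6.0, 9.0 |
| Inpatient use | Self-directed; visits not tied to sessions | 2.0, 6.0 |
| Optional home use, up to 14 days | No | 6.0 |

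The sentence holds for the first row only.

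**Step 2. Share of sessions unattended.** Assume 1 tutorial session, 7 preoperative sessions, one session on each of k inpatient days and h sessions after discharge. Length of stay is not given beyond a minimum of one night, so k is varied from 1 to 7.

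If, generously, every inpatient session is observed, the share is (7 + h)/(8 + k + h):

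- h = 0: k = 1 gives 7/9 = 78%; k = 3 gives 7/11 = 64%; k = 5 gives 7/13 = 54%; k = 7 gives 7/15 = 47%.
- h = 14: from 21/29 = 72% (k = 7) to 21/23 = 91% (k = 1).

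If inpatient use is self-directed, as section 2.0 says, the share is (7 + k + h)/(8 + k + h). Its lowest value is 8/9 = 89%, at k = 1 and h = 0. Most use is therefore unattended, except for a week-long stay with every inpatient session observed and no later home use.

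**Step 3. Scheduled home sessions before surgery, at one a day.**

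- Aim 2 VR-BF arm: 35 x 7 = 245. At the adherence threshold of 5 of 7 days, 35 x 5 = 175. If 80% of patients (28) reach it and the rest do none, 28 x 5 = 140.
- Aim 1: 12 x 7 = 84 to 32 x 7 = 224.

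These count exposure, not missed events. The Aim 2 schedule may change after Aim 1.

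**Step 4. Where a mild symptom could be recorded.**

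- Logs: in Aim 1, "They will use a log to record their VR-BF usage (date, time, and duration". In Aim 2, the described items are use, pain, anxiety and opioids. No symptom item is described.
- Instruction to patients: "Patients will be instructed to remove the device should any discomfort or side effects occur". Nothing tells them to report it.
- Discharge visit: questionnaire and interview, after all preoperative and inpatient use. This route depends on recall.
- After discharge: a clinic visit with recorded questions about home use, and a parent survey. Adverse events are not named. Section 6.0 also says "Patients will be asked to complete a survey at the end of study participation", which might fall after home use, but the Aim 2 text places the questionnaire before discharge.

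**Step 5. What incomplete capture could do (illustration only).** Let p be the true proportion of patients with a mild event and s the proportion of those recorded; both are assumptions. The chance that an arm of 35 records none is (1 - p x s)^35:

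| p | s = 100% | s = 50% | s = 25% |
|---|---|---|---|
| 5% | 17% | 41% | 64% |
| 10% | 2.5% | 17% | 41% |
| 20% | 0.04% | 2.5% | 17% |

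One unrecorded patient moves the arm's rate by 1/35 = 2.9 points, or 1/28 = 3.6 points after 80% retention.

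**The case against.** The strongest reply accepts the wording error and contests the rest. The plan names adverse events in the CRF list and in Table 3. Tolerability is defined by adverse events and compiled from a questionnaire and interview that follow every preoperative and inpatient session, so this is a direct route. Inpatient visits deal with any problems, reasons for non-adherence are collected, and section 25.0 has the study doctor called for signs needing attention. The interview guide, questionnaires, CRF and Data Safety Monitoring Plan are not among the documents, and a protocol narrative need not list every form field.

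Most of this stands. A reader might infer that the plan does not collect adverse events, or that mild ones will be missed. The documents support neither: collection is committed to, and the absence of a symptom line from the narrative does not show that the forms lack one. A reader might also infer that the serious-event benchmark is compromised or that patients are left unprotected. A serious event is unlikely to go unnoticed, patients with seizure disorder or significant motion sickness are excluded, and patients are told to take the headset off.

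The reply does not remove three things. The CRF item is permissive, discharge collection depends on recall, and use after discharge has no named adverse-event question.

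**Conclusion.** The monitoring sentence is wrong as written. This rests on the protocol text alone, and nothing in the documents qualifies it. On the assumptions shown, 47% to 91% of sessions are unattended even if every inpatient session is observed, and at least 89% if inpatient use is self-directed.

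The recording point is narrower. As described, capture of mild events from unattended sessions rests mainly on recall at discharge, with no named question for later home use. Under-recording is possible, its extent cannot be computed from the documents, and unseen forms may already prevent it. Only the descriptive adverse-event rate is exposed. The benchmark of under 1% serious events, the sample size and the decision rules are unaffected.

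**What to change.** Reword section 15.0, for example:

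> Researchers will supervise the tutorial and training session, in person or virtually. All other use, at home and in hospital, is independent. Patients and parents will be told to take the headset off if symptoms occur and to report them to the study team.

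Add one symptom line (yes/no, type) to the daily logs or reports in both arms. For control patients, whose report is generated by the application, this would be a short separate item. Ask one adverse-event question at the first postoperative clinic visit, or at whatever contact replaces it. If a form or the Data Safety Monitoring Plan already does this, cite it in the Tolerability text of section 6.0 and in section 15.0 instead.

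No extra visits or staff are needed. Patients already enter 2 scores x 4 time points = 8 ratings per postoperative session, so a daily line adds little. The costs are a slight added burden in a trial where burden is an outcome, and a possibly higher reported adverse-event rate.

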16.0 Potential Benefits to Subjects*

Individual study participants may derive direct benefit from participation in the study as the addition of VR or Manage My Pain may enhance standard pain management strategies and result in decreased pain intensity and unpleasantness and anxiety at the time of participation in the study. Participants may also have a longer lasting benefits, but these are currently unexplored,

Feasibility and Acceptability of Technology-Based Interventions in the Perioperative Setting

and this exploration will be part of future studies. Should VR show to be a useful tool to augment pain control, we hope that this technology will ultimately be offered to all pediatric patients coming in for surgery to assist with postoperative pain control. Participation in the study may also decrease medication consumption; however, this potential benefit will be assessed in subsequent studies using the treatment protocol developed in this proposed work. Patients may receive a stipend for participation, not to exceed a total of \$100 per patient.

17.0 Data Management* and Confidentiality

Aim 1:

Data analysis. Statistical analysis will be done using SAS 9.4 (Cary, NC). Demographic and baseline characteristics will be summarized for all patients (*categorical variables*: frequency and percent; *continuous variables*: mean \pm standard deviation (SD) or median and interquartile range (IQR)).

Qualitative analysis. Qualitative data will be collected via questionnaires and a semi-structured interview (see Appendix 1 for the interview guide and Appendix 2 for the questionnaires) conducted by a trained CRC. The interview script creates a framework for the discussion with further probing based on patients' responses to elicit a rich and informative description of their experiences and perceptions. Interviews will be recorded, assigned an identification number to anonymize content, and transcribed for coding. Each transcript will be independently reviewed by two trained coders and line-by-line content will be analyzed using *a priori* themes evaluating the acceptability and satisfaction with content (understanding, difficulty level, ease of use), feasibility of practice (both at home after preoperative training and after surgery), and perceived helpfulness in reducing pain and distress after surgery. Results will be analyzed and reviewed by the study team after each cohort of four patients has completed Aims 1a and 1b so that iterative changes can be made to refine the protocol (e.g., improvements to the education component, involvement of parents, device adjustments, recommendations for duration and frequency of use postoperatively, etc.) before the next group of four patients is enrolled.

Quantitative analysis (dose). Data will be collected on number of daily practice (preoperative) and therapy (postoperative) sessions completed by each patient, duration of each session, and changes in HRV and respiratory rate parameters over time. We will also assess the total daily dose of sessions by totaling the duration of all sessions per day and assessing the mean and variability of the daily dose. These quantitative data together with quantitative responses from the questionnaires and interviews will be summarized using frequency and percent for categorical variables and mean \pm SD or median and IQR for continuous variables. For variables measured multiple times per participant (duration of each practice/therapy session, changes in HRV and respiratory rate), within- and between-subject summary measures of location and variability will be derived and examined.

Sample size. No statistical power analysis was done to determine the sample size for Aim 1. Rather, sample size determination was based on our extensive pilot work and clinical experience with the population along with the team's expertise in protocol refinement studies in intervention development.

Anticipated outcomes. At the end of Phase 1, we anticipate having a refined treatment protocol for preoperative education and training, and postoperative application of VR-BF. This protocol will be piloted in Phase 2. Results from Aim 1 will provide a preliminary study protocol and manual of procedures for the clinical efficacy trial that will be finalized at the end of Aim 2.

Feasibility and Acceptability of Technology-Based Interventions in the Perioperative Setting

Aim 2:

Data analysis. Phase 2 is a single-center, randomized, two-arm, parallel-group, single blinded trial to assess the feasibility and acceptability of the treatment protocol designed in Aim 1. We will ensure study transparency, describing recruitment, enrollment, and outcomes in a Consolidated Standards of Reporting Trials (CONSORT) diagram^{106,120} and provide detailed descriptions of the intervention and active control. Demographic and baseline characteristics will be summarized for all patients and within each study group (categorical variables: frequency and percent; continuous variables: mean \pm SD or median and IQR).

Quantitative analysis. We will assess measures of feasibility and acceptability for each arm.

Feasibility. We will calculate descriptive data on 1) How many patients are screened per month; 2) Percentage of patients meeting eligibility criteria; 3) Percentage of eligible patients approached, enrolled, and randomized; 4) Percentage of patients completing Phase 2; and 5) Percentage of patients adhering to preoperative education and postoperative application of VR-BF as defined in the study measures. For each measure, the rates, variances, and two-sided 95% confidence interval (CI) will be reported. Each CI will be examined to determine if the hypothesized value of 80% is contained within the interval. This data will also be used to generate a diagram of participant flow. Because this is a feasibility study, we will not conduct statistical tests on the clinical outcomes collected for exploratory purposes (pain and anxiety ratings, opioid use). We will analyze this data using descriptive measures stratified by treatment arm. **Acceptability.** We will calculate descriptive data on 1) Treatment/study burden: number and percentage of patients completing all study measures; 2) Tolerability: number and percentage of patients experiencing AEs; and 3) Any quantitative data of satisfaction and treatment credibility from questionnaires and semi-structured interviews. For each of these measures, the rates, variances, and two-sided 95% CI will be reported. The CI for treatment/study burden will be examined to determine if the hypothesized value of 80% is contained within the interval. Qualitative treatment credibility and parent/patient satisfaction data will be assessed qualitatively as described below.

Dosing. To finalize VR-BF dosing prior to the efficacy trial, data will be collected on the number of daily practice (preoperative) and therapy (postoperative) sessions completed by each patient, duration of each session, changes in HRV and respiratory rate, and achievement of target HRV and respiratory rate parameters. We will also assess the total daily dose of sessions by totaling the duration of all sessions per day and assessing the mean and variability of the total daily dose. Achievement of target physiological parameters will be assessed by calculating the percentage of time a patient spends within specified targets for each session. Consistency in achieving target HRV and respiratory rate parameters will be defined as a binary outcome (yes/no) when the target range is achieved $\geq 75\%$ of the time during use (by session and by day). We will run descriptive statistics on duration of each session stratified by sessions achieving consistency (or not) and on frequency and duration of daily use by days achieving consistency (or not). Mean duration per session and mean duration and frequency per day in the group achieving consistency will be used to guide minimal dosing in the efficacy trial. **Exploratory analysis.** We will examine the association of VR-BF dose (frequency and duration of use) with the change in target physiological parameters to help identify the minimal dose (frequency and duration of use) required to reach consistency in achieving these targets. We will also examine the correlation between pain score reduction and VR-BF use (frequency and duration). We will calculate mean changes in pain score before and after VR-BF and mean frequency and duration of VR-BF use for each patient. We will visualize any correlation using a scatter or box plot and quantify the correlation using Spearman or Pearson correlation coefficients between two continuous variables

Feasibility and Acceptability of Technology-Based Interventions in the Perioperative Setting

and two sample t-tests or Wilcoxon rank-sum tests, as appropriate, between a continuous and categorical variable. Regression on changes in pain score will be used to examine linear or nonlinear correlations between pain reduction and VR-BF use. The same analysis will be repeated for opioid use (mg/kg/day) and patient-reported anxiety scores.

Qualitative analysis. From the questionnaires and semi-structured interviews, we will compile data on satisfaction, credibility, and tolerability as well as additional feasibility data. This qualitative data will be analyzed in the same way as in Aim 1.

Sample size. Seventy subjects will be enrolled and randomized to one of two study arms: intervention and active control. As this is a pilot feasibility and acceptability study, no confirmatory hypothesis testing will be done. Our sample size is based on estimation of two-sided CIs for one proportion with exact formula of the binomial probabilities. To estimate a 95% CI with targeted width of 0.22 and an assumed proportion of 80%, we will need a sample size of 70 (35 per group), resulting in a total of 56 patients (28 per group) included in the analysis after 80% retention.

Anticipated outcomes. We anticipate creating a final VR-BF study manual that will define study procedures for an efficacy trial and provide key pilot data for future grant applications. By the end of Phase 2, we expect to have 1) A defined patient population with clearly delineated eligibility criteria; 2) A clearly delineated preoperative education and training protocol for VR-BF/active control; 3) A dosing strategy (frequency, duration) for postoperative administration of VR-BF/active control; 4) Feasibility and acceptability data for VR-BF/active control; and 5) A preliminary assessment of key outcome measures (pain, anxiety, opioid consumption) to be evaluated in the efficacy trial.

Data Safety:

Data confidentiality will be maintained by data being stored in a password protected computer and any hard copies of patient information stored in a locked office. Data will be transmitted to a password-protected Nationwide Children's computer for further analysis. Data held in REDCap is deemed secure. All individuals using and interacting with this data will be trained appropriately and a member of the study team. Any data transmission will occur via secure emails (not personal). Proper agreements have been executed to cover the sharing of de-identified data from REDCap with a statistician at CCHMC. Data will be de-identified by selecting the option to export data directly from REDCap with all known identifier fields (date, name, address, MRN, etc.) removed. The exported data set will then be shared with CCHMC. Data will be stored for the duration of the study and analysis/presentation up to the time period specified by the IRB.

